6.2.3 PRODUCT STORAGE AND STABILITY

"gammaCore should be stored at room temperature away from moisture • Range: 0°C to 38°C (32°F to 100°F), Humidity: 10% to 90%, Barometric Pressure: 80 to 101 kPa Replace cap after each use, Store the device in such a way (eg, drawer or shelf) that the cap remains in place and are not accidentally removed". (19)

6.2.4 PREPARATION

Per the gammaCore pamphlet "Charge your device before first use. Allow 6 to 7 hours for a full charge. High temperatures may increase the charging time. If the device has no charge, it takes only a few minutes to charge an additional two to three treatments. Monitor battery life and charge as needed to maintain adequate number of treatments on device" (19)

6.3 MEASURES TO MINIMIZE BIAS: RANDOMIZATION AND BLINDING

To minimize bias, this will be a randomized controlled trial. Patients will be randomized using variable block design, assigning patients 1:1 to the treatement group n-VNS and sham group, with concealment of allocation. Participants and the provider assessing the pain scale, providing the pain killers and assessing for adverse events will be blinded.

6.4 STUDY INTERVENTION COMPLIANCE

The trial will be evaluated on a daily basis if there are active patients enrolled. The principle investigator will meet monthly with the study coordinator, research assistant and co-investigators evaluating the adherence with the study protocol.

The vital signs, medication administered, and pain assessment will be recorded as standard of care in our electronic medical record SUNRISE.

6.5 CONCOMITANT THERAPY

Patients will be given standard of care medication for delayed cerebral ischemia prophylaxis and opiates and acetaminophen for pain control. Opiate addicts and patients on chronic opiates at home will be excluded.

6.5.1 RESCUE MEDICATION

Rescue pain killers will be given per standard of care in both groups.

7 STUDY INTERVENTION DISCONTINUATION AND PARTICIPANT DISCONTINUATION/WITHDRAWAL

7.1 DISCONTINUATION OF STUDY INTERVENTION

The study intervention will be held during procedure days, or if the participant gets intubated, or is in shock (cardiogenic, distributive or septic). During non-procedure days, or once extubated and stabilized and participant becomes alert the study intervention can be resumed.

In addition, as stated earlier, if HR< 60 beats/min, SBP<100 mm HG, or MAP< 60 mm HG and oxygen saturation < 90 %, the intervention will be postponed.

If hemodynamic instability or unstable arrhythmia occur during the VNS, and is thought to be due to the VNS by the investigator, the participant will be discontinued from the study procedure, however, will be followed until discharge from the hospital.

If a clinically significant finding is identified (including, but not limited to changes from baseline) after enrollment, the investigator or qualified designee will determine if any change in participant management is needed. Any new clinically relevant finding will be reported as an adverse event (AE).

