4.4 END OF STUDY DEFINITION

The study intervention will be up to 10 days in length. Vagus stimulation will be performed 4 times daily (approximately at 6:30AM, 11:30AM, 4:30PM and 9:30PM). Data collection will continue till hospital discharge. If the participant becomes hemodynamically unstable, defined as hypotension requiring vasopressors the VNS will be held for safety purposes. However, it will be resumed, once the patient is stabilized, off vasopressors for 48 hours. If the patient is being hemodynamically augmented for symptomatic vasospasm, n-VNS will not be withheld as the beneficial effects of n-VNS on symptomatic vasospasm will be investigated in this study.

Participants must fulfill all of the inclusion criteria in order to be eligible for the study:

- Established signed and dated informed consent form
- Can be enrolled within 5 days of cerebral aneurysm treatment.
- CT of the head revealing blood in the subarachnoid space
- Subject has ruptured cerebral aneurysm or SAH patients who do not have vascular malformation on cerebral angiogram.
- Subject is male or female 18 -75 years of age
- Subject is alert able to verbalize pain at the time of enrollment
- Subject reports pain of 7 and greater on a 10 Point Pain numeric rating scale or presenting with severe headache.
- Female of reproductive age must have a negative pregnancy test (Urine or blood test)

nVNS will only be performed if vital signs are stable (HR>60, SBP> 100 mmHg, MAP> 60 mmhg, and saturation > 90% on room, nasal cannula or face mask). Then the vagus nerve will be stimulated.

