8.2 SAFETY AND OTHER ASSESSMENTS

nVNS has been proven to be safe. However, the risks of VNS in SAH population are not known. In order to minimize the risks, if an aneurysm has been identified to be the cause of the SAH, patients will only be enrolled if the aneurysm has been completely treated. This information will be pulled from the medical record. Past medical and surgical history, respiratory and hemodynamic state will be pulled from the medical record. Vital signs and neurologic examinations are usually performed every 1 to 4 hours depending on the acuity of each case, and pain assessment evaluated every 4 hours and as needed. In the NSCU, patients are on continuous ECG analyzes via telemetry. Stimulation will only be given if HR >60 and the SBP>100 mmHg, MAP> 60 mmHg and oxygen saturation is >90% for safety concerns. The presence of intolerable pain at the stimulation site, skin irritation, hoarseness, and change in the taste, shortness of breath, chest pain, nausea, and vomiting will be evaluated.

Safety outcomes:

- Rate of Symptomatic bradycardia defined as a drop in HR to less than 60 beats per minutes with symptoms, not due to nimodipine. The timing of nimodipine relative to the VNS will be recorded. All patients are on telemetry during the stimulation.
- Rate of drop in blood pressure, defined as a drop in blood pressure requiring fluid resuscitation or vasopressor support thought to be due to the device.
- Rate of side effects: presence of intolerable pain at the stimulation site, skin irritation, nasopharyngitis, hoarseness, dysgeusia, shortness of breath, chest pain, nausea and vomiting.

Figure

Days 1-3	Screening			
 Total n=40 Obtain informed consent Screen potential participants by inclusion and exclusion criteria Obtain history, document Randomize 				
Days 2-4 till discha from ICU	rge Baseline assessments/ Study Intervention			
 Obtain daily cumul Evaluate presence Evaluate seizures d Complete vital sign Questionaire for sign 	as before and after each stimulation and daily trend de effects from VNS post every stimulation scranial dopplers (TCD) comatic vasospaspm I fever			
Discharge from the hospital or day 10 post-ictus				

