8.3.5 SERIOUS ADVERSE EVENT REPORTING

The study clinician will report to the IRB any serious adverse event related or potentially related to the study intervention. All serious adverse events (SAEs) will be followed until satisfactory resolution or until the site investigator deems the event to be chronic or the participant is stable.

POTENTIAL SERIOUS ADVERSE EVENT mentioned in section 8.3.2

Monitoring: Participants will be on continuous telemetry recording continuously the EKG, respiratory rate, oxygen saturation, Blood pressure will be recorded one-hour post-stimulation and 1-4 hours afterwards. Vital signs will be recorded before and directly after stimulation, the medical professional will be at bedside during the stimulation monitoring any side effect. Vital signs and neurologic examination are evaluated every 1-4 hours and as needed afterwards. The VNS will be performed in the intensive care unit setting, where personnel are trained in cardiopulmonary resuscitation and treating hemodynamically unstable patients.

Actions:

- Participants must have stable vital signs (SBP> 100mmHg, MAP>60 mmHg, HR> 60 beats/minute, oxygen saturation > 90%, not on mechanical ventilation) before the vagus nerve is stimulated. If unstable vital signs, the stimulation will be skipped, until the patient is more stable.
- If the participants develop a life-threatening arrhythmia thought to be due to the VNS, subject will be taken off therapy, but will continue to be followed until end of study.
- If the participants get intubated or develops hemodynamic shock due to the natural history of the disease, the subject will be taken off the therapy.

The study investigator shall complete an Unanticipated Adverse Device Effect Form and submit to the reviewing Institutional Review Board (IRB) as soon as possible, but in no event later than 7 working days after the investigator first learns of the effect. The principle investigator is responsible for conducting and evaluating any unanticipated adverse device effect and shall report the results of such evaluation to the reviewing IRB and participating investigators within 7 working days of the event.

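### After vasopressor-requiring hypotension attributed to the device, protocol section 4.4 says resume and 7.1 says discontinue; as worded, 7.1 also misses events after a session

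*Protocol*

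**What the plan says.** Three protocol sections say what happens to stimulation after a hemodynamic event. The SAP contains no such rule.

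- **Section 4.4 (End of Study Definition).** "If the participant becomes hemodynamically unstable, defined as hypotension requiring vasopressors the VNS will be held for safety purposes". It continues: "However, it will be resumed, once the patient is stabilized, off vasopressors for 48 hours". The cause of the hypotension is not mentioned. The section makes one express exception, for blood pressure augmentation in symptomatic vasospasm, and none for events caused by the device.
- **Section 7.1 (Discontinuation of Study Intervention).** "If hemodynamic instability or unstable arrhythmia occur during the VNS, and is thought to be due to the VNS by the investigator", then "the participant will be discontinued from the study procedure, however, will be followed until discharge from the hospital". The same section has a separate hold for procedure days, intubation and shock, after which "once extubated and stabilized and participant becomes alert the study intervention can be resumed".
- **Section 8.3.5 (Serious Adverse Event Reporting, Actions).** "If the participants develop a life-threatening arrhythmia thought to be due to the VNS, subject will be taken off therapy", with follow-up to the end of the study. It states no window relative to stimulation and no stopping rule for hypotension caused by the device.

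Two further places bear on the point. Section 8.2 lists as a safety outcome the rate of a "drop in blood pressure requiring fluid resuscitation or vasopressor support thought to be due to the device", with no time limit, and the SAP repeats it under its analysis of safety variables. Section 7.2 permits, but does not require, the investigator to withdraw a participant because of an adverse event.

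**The concern.** Staff caring for a participant whose blood pressure fell to the point of needing vasopressors, and whose event the investigator attributes to the device, would find two instructions. One restarts stimulation after a set interval and the other ends it. Both are mandatory in form, and neither says which prevails. If the fall came shortly after a session rather than in it, the discontinuation sentence does not literally apply and the resume rule is left standing alone.

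What is at stake is re-exposure to a device that the treating team believes caused the event, in a population for which section 8.2 says the risks are not known. Two participants with the same event could be handled differently according to which section was read. That would make exposure inconsistent and could affect who enters the SAP's primary efficacy set.

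**Working it through.** The plan gives no figure to reproduce on this point, so the check is mainly a comparison of texts.

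**Step 1: do 4.4 and 7.1 concern the same event?** Only section 4.4 defines hemodynamic instability, and it does so as hypotension needing vasopressors. Section 7.1 uses the same term without redefining it, and adds two conditions: timing and attribution to the device. Every 7.1 instability event that meets the 4.4 definition is therefore also a 4.4 event.

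**Step 2: the rules side by side, for events attributed to the device.**

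| Event | 4.4 | 7.1 | 8.3.5 | Result |
|---|---|---|---|---|
| Hypotension on vasopressors, during stimulation | Hold, then resume | Discontinue | No rule | Direct contradiction |
| Same, after the session | Hold, then resume | Discontinuation sentence not met as worded | No rule | Resume rule stands alone |
| Unstable arrhythmia, during stimulation | Not covered | Discontinue | Off therapy if life-threatening | Agree |
| Same, after the session | Not covered | Discontinuation sentence not met as worded | Off therapy if life-threatening | Scope differs; no conflict |

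**Step 3: does the protocol expect device-attributed events after a session?** Yes. Section 8.3.5 has blood pressure recorded an hour after stimulation and again in the following hours. Section 8.3.3 collects reportable events for up to three days past the last stimulation day, or to discharge if sooner. Section 8.4.3 allows three days to establish that an unanticipated problem is due to VNS. The outcome in 8.2 has no window.

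**Step 4: does a different reading of *during* help?** If it means the stimulation itself, the second row is a gap. If it means the whole course of therapy, the gap closes, but the contradiction in the first row then extends to post-session events.

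**Step 5: arrhythmia.** Section 8.3.2 gives hemodynamically unstable arrhythmia as an example of a life-threatening event, so the triggers in 7.1 and 8.3.5 are nearly equivalent and the action is the same. Two differences remain: the window (*during* against none) and the end of follow-up (hospital discharge against end of study).

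**Step 6: reach into the analysis.** The SAP makes the mITT set primary for efficacy and requires at least 7 treated days. Assume the protocol's maximum of 10 intervention days and no other missed days.

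- Under 7.1, a participant discontinued before 7 treated days cannot enter the set.
- Under 4.4, with v days on vasopressors and then 48 hours (2 days) off them, the days left for treatment are at most 10 − v − 2 = 8 − v. This is at least 7 only if v ≤ 1.

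The choice of rule can therefore decide mITT membership, but only for an early event with about a day or less on vasopressors. For v > 1 the gap is v + 2 > 3 consecutive days, at which point 7.2 also permits withdrawal.

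**The case against.** The best reply is that 4.4 is a general hold placed under an end-of-study heading, while 7.1 is the dedicated discontinuation section and adds a causation condition. The specific rule would ordinarily displace the general one. That is a fair reading and would settle the in-session case. But the text does not say so, and 4.4 shows that its drafters wrote an exception where they wanted one. On the literal meaning of *during*, this reading also leaves the post-session case under the resume rule.

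A second reply is that other safeguards make automatic re-exposure unlikely. The last paragraph of 7.1 requires the investigator or a designee to decide whether management should change after a significant finding. Section 7.2 allows withdrawal, vital-sign limits must be met before every session, and section 10.1.6 provides weekly unblinded review of aggregate safety data. This lowers the practical risk. It does not reconcile two mandatory sentences, because 7.2 is discretionary and the vital-sign check asks about present stability, not about cause.

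Several stronger readings are tempting but not supported:

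- *That a section restarts stimulation after an arrhythmia caused by the device.* None expressly does; 4.4 speaks only of hypotension.
- *That 7.1 and 8.3.5 set conflicting arrhythmia thresholds.* Section 8.3.2 makes them nearly equivalent.
- *That this is the only individual safeguard against toxicity.* The provisions just listed show otherwise.
- *That nearly all device-caused events escape 7.1 because stimulation fills few minutes of the day.* That is a share of clock time, not of events, and section 8.4.3 says most side effects arise while stimulation is being given.
- *That the primary safety endpoint would be distorted.* It is an incidence of device-related serious events. A participant whose first event was judged serious is already counted, and re-exposure cannot change that. If the first event was not judged serious, a later one could add to the count, but nothing in the documents shows that this would happen.

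A neighbouring discrepancy is separate from this point: for intubation or shock due to the disease, 7.1 holds and allows resumption while 8.3.5 takes the subject off therapy.

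**Conclusion.** The concern holds for one event: hypotension needing vasopressors that is attributed to the device. During stimulation, 4.4 and 7.1 give opposite mandatory instructions. After a session, 7.1 read literally falls away, 4.4 resumes, and 8.3.5 is silent. For arrhythmia there is a difference in window and follow-up wording, not a contradiction over whether to stop.

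The number of participants affected cannot be estimated, since the documents give no expected rate of device-attributed hypotension in this population. The effect on the primary efficacy set is limited to the circumstances worked out above.

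The conclusion assumes that *hemodynamic instability* in 7.1 carries the 4.4 definition and that *discontinued* means stimulation is not restarted. The second is an inference: 7.1 does not say permanently, but it uses held and postponed elsewhere as different terms. The point implies no view on which clinical rule is right.

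**What to change.** Reconcile sections 4.4, 7.1 and 8.3.5 into one rule, stated once and cross-referenced from the other places. It should:

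- say whether the 4.4 hold-and-resume provision applies when instability is attributed to the device;
- use one event window, consistent with the safety outcomes in 8.2 and the SAP;
- use the same arrhythmia wording and the same end of follow-up throughout.

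The investigators and the IRB should choose the clinical content. The disease-related intubation and shock wording in 7.1 and 8.3.5 can be reconciled in the same edit.

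The cost is a wording amendment with IRB review and a short staff briefing. No extra participants, procedures or data collection are needed.

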7.2 PARTICIPANT DISCONTINUATION/WITHDRAWAL FROM THE STUDY

Participants are free to withdraw from participation in the study at any time upon request. An investigator may discontinue or withdraw a participant from the study for the following reasons:

- Significant study intervention non-compliance
- If any clinical adverse event (AE), laboratory abnormality, or other medical condition or situation occurs such that continued participation in the study would not be in the best interest of the participant
- Disease progression which requires discontinuation of the study intervention
- If the participant meets an exclusion criterion (either newly developed or not previously recognized) that precludes further study participation
- Participant unable to receive the study intervention for more than 3 consecutive days

The reason for participant discontinuation or withdrawal from the study will be recorded on the Case Report Form (CRF). Subjects who sign the informed consent form but do not receive the study intervention may be replaced. Subjects who sign the informed consent form, and receive the study intervention, and subsequently withdraw, or are withdrawn or discontinued from the study, will not be replaced.

7.3 LOST TO FOLLOW-UP

There should be no loss of follow up as this is an inpatient study. The study will last for up to 10 days.

8 STUDY ASSESSMENTS AND PROCEDURES

8.1 EFFICACY ASSESSMENTS

Per standard of care, patients presenting with signs of SAH like acute severe headache, will get a diagnostic head CT which confirms blood in the subarachnoid space. If patients have symptomatic hydrocephalus (altered mental status with CT head consistent with hydrocephalus) an external ventricular drain will be placed. Most patients will get either a CT angiogram or a conventional angiogram to rule out a vascular malformation, especially if there is no history of trauma. If an aneurysm is detected, the standard of care is to treat it as soon as possible. Usually, an aneurysm iseither coiled or clipped (craniectomy or craniotomy). Every patient admitted with subarachnoid hemorrhage will get graded accordingly to their headache intensity, level of consciousness and neurologic deficits with the Hunt Hess grade (table 2). Their CT scans also get graded (modified fisher scale mFS) according to the thickness and location of blood (table 3). All subarachnoid hemorrhage (unless there is minimal amount of blood and no vascular malformation) are admitted to the Neurosurgical care unit (NSCU). Detailed physical examination, including the NIHSS, history, including medication history, past medical, surgical history, and social history are recorded in the medical records. North Shore University hospital NSCU is the referral center for most of the hospitals in Northwell health care system. Most aneurysmal SAH patients get transferred to our unit. Per standard of care, all women of child bearing age, admitted to the NSCU get a urine or blood pregnancy test, patients suspected of abusing drugs get urine toxicology. Once in the NSCU, patients get vital signs and neurologic assessment every hour, and pain assessment every 4 hours and as needed. The length of stay in the intensive care unit depends on the amount of blood on the head scan (mFS). Patients with higher mFS are more prone to get delayed cerebral ischemia. As a result, per standard of care, patients with SAH get almost daily transcranial dopplers to monitor for cerebral vasospasm, frequent head scans, occasionally brain perfusion studies and MRI of the brain. Patients are monitored for central fever (vital signs, blood cultures), cerebral salt wasting with frequent BMP and urine output measurements, seizures with PRN electroencephalograms (EEG). Once out of the critical care period, (vasospasm usually starts at day 3 post bleeding and peaks at day 10), patients get transferred to a regular neurosurgical floor before being discharged home or to rehabilitation. On average patients stay in the NSCU between 2-21 days. All patients admitted to the NSCU with SAH will be screened and evaluated for the inclusion and exclusion criteria after obtaining an informed consent.

Screening involves reviewing the medical records following HIPPA regulation for: Age, gender, ethnicity, presence of aneurysm, day of rupture, etiology of the SAH if not aneurysmal, radiologic (Angiogram, CT head) and medical history before and after the aneurysm is secured, Glasgow coma score before and after aneurysm repair, modified fisher scale (mFS), Hunt-Hess grade (HHS), time of ictus, history of alcohol and drug abuse, presence of hydrocephalus on head CT, presence of an external ventricular drain (EVD), date of EVD placement, new HHS after EVD placement, clipping or coiling. Medical records will be reviewed for the past medical history (pacemaker, defibrillator, history of CHF, arrhythmias, cervical carotid disease, history of a headache disorder like migraine or cluster headache), physical examination, labs will be reviewed which includes but not limited to pregnancy test and urine toxicology. Headache intensity and opiate, steroids and acetaminophen usage are recorded in the electronic medical record. The presence of vasospasm and delayed cerebral ischemia will be noted. Once found eligible satisfying the inclusion and exclusion criteria, and informed consent signed, patients will be randomized to either the treatment group or the control group. The same data will be recorded for both groups. The treatment period will start once admitted in the NSCU and will last for up to 10 days.

During the NSCU stay, patients areevaluated for pain every 4 hours. If vital signs are stable (SBP> 100 mmHg and HR> 60 beats per minutes with no arrhythmia on telemetry, MAP> 60 mmHg and oxygen saturation > 90%) patient will receive either the treatment (nVNS) or the Sham device every 5 hours. Headache intensity will be evaluated every four hours. In addition, vital signs will be noted just after stimulation, and hourly afterwards or as ordered by the physician. The daily mean morphine equivalence dosage will be recorded. Concomitant medications will be recorded.

During the ICU length of stay, the following will be assessed and recorded per standard of care :

- Transcranial dopplers (TCD)
- Neuroimaging (CT head, MRI brain, angiograms, CT perfusion with permeability study)
- EVD weaning and day of start of weaning
- Presence of vasospasm, delayed cerebral ischemia, Central fever, Cerebral salt wasting. These are usually recorded in the medical record.
- Urinary retention documented as frequent straight catheterization for more than 3 days
- Constipation evaluated by the need for enema, suppository, lactulose or magnesium oxide administered
- Blood tests, CSF studies
- EEG results
- Neurologic examination including Glasgow coma score, and NIHSS
- Delirium score

When Transcranial dopplers are being done as per standard of care, we will assess the changes in transcranial velocities around the time of the stimulation of the Vagus nerve.

When possible, we will draw blood or in case there is an EVD we will also collect CSF for biomarkers. Not more than 5 ml of blood will be drawn before the 11:30 am stimulation session of the Vagus nerve. This will be repeated approximately 24 hours later, at 11:30 am post VNS stimulation session. This might be repeated on days 5 and 7 post-ictus In case there is an EVD, 2 cc of CSF from the drain and 20 cc of CSF that is otherwise discarded will be drawn before the 11:30 am stimulation session of the Vagus nerve. Another 2 cc of CSF from the drain and 20 cc of CSF that is otherwise discarded will be drawn before the 11:30 am stimulation session of the Vagus nerve. Another 2 cc of CSF from the drain and 20 cc of CSF that is otherwise discarded will be drawn approximately 24 hours later, at around 11:30 am post VNS stimulation session. This might be repeated on days 5 and 7 post-ictus.

The CSF will not be taken from the proximal port of the EDV unless it is being tested for CSF cell count or cultures as per standard of care. This is in order not to increase the risk of infection.

Deidentified blood and CSF will be sent to [name], academic chief in the department of stroke and vascular neurology, Yale, [name].

IF CT perfusion is being performed per standard of care between days 3-10, blood brain permeability will be evaluated and results will be compared between the sham group and the active device group.

During the period of the study after the patients are discharged from the ICU to the Neurosurgical floor, we will evaluate their daily headache intensity and morphine equivalence dosage, in addition to their TCD results, Neuroimaging and EEG results, neurologic examination and vital signs.

Table 2: Hunt-Hess Score in aneurysmal SAH: (26, 27)

- 1. Asymptomatic, mild headache, slight nuchal rigidity
- 2. Moderate to severe headache, nuchal rigidity, no neurologic deficit other than cranial nerve palsy
- 3. Drowsiness, confusion, mild focal neurologic deficit
- 4. Stupor, moderate-severe hemiparesis
- 5. Coma, decerebrate posturing

Table 3: Modified Fisher Scale:(28)

- grade 0: no subarachnoid hemorrhage (SAH), no intraventricular hemorrhage (IVH)
- grade 1 focal or diffuse, thin SAH, no IVH
- grade 2 thin focal or diffuse SAH, IVH present
- grade 3 thick focal or diffuse SAH, no IVH grade 4: thick focal or diffuse SAH, IVH present

